5 SELECTION OF STUDY POPULATION

5.1 NUMBER OF SUBJECTS

Up to eighty four (84) healthy subjects will be enrolled in the study

5.2 INCLUSION CRITERIA

1. Healthy males and females between 20 and 40 (inclusive) years of age.
2. Subjects who provide written informed consent to participate in the study.
3. Subjects in general good health in the opinion of the investigator as determined by medical history, vital signs and a physical examination.
4. No clinically significant abnormalities in hematology, blood chemistry, or urinalysis lab tests at screening.
5. Women of child-bearing potential must practice an acceptable method of birth control (as specified in Section 8.2) or practice abstinence during the study period or be surgically sterilized, from screening visit throughout the treatment phase and for 28 days after the last injection and agree to undergo repeated pregnancy tests.
6. Subjects must be able to understand the requirements of the study and must be willing to comply with the requirements of the study.

5.3 EXCLUSION CRITERIA

1. Known history of significant medical disorder, which in the investigator's judgment contraindicates administration of the vaccine or may interfere with the subject's compliance or the interpretation of study assessment parameters.
2. Any clinically significant abnormality upon physical examination or in the clinical laboratory tests at screening visit.
3. Treatment with immune suppressive agents.
4. Chronic administration (defined as more than 14 days) of immunosuppressants or other immune-modifying drugs within six months prior to the first vaccine dose.
5. History of HBV infection or confirmed exposure to hepatitis B virus.
6. Previous vaccination against Hepatitis B.
7. Positive for HBsAg, anti-HBsAg antibodies, anti-HBc antibodies, anti-HCV antibodies or anti- HIV antibodies.
8. Drug abusers
9. Known hypersensitivity or allergy to any component of the study vaccine.
10. BMI < 18.5 or ≥ 30 Kg/m².
11. Known concomitant disease or any other medical condition that is considered by the investigator likely to interfere with the subject's compliance or the interpretation of study assessments.
12. Any acute illness (e.g. acute infection) within 48 hours prior to the first study drug administration that is considered of significance by the Principal Investigator.
13. Female subjects: pregnant, lactating or planning a pregnancy.

	Protocol No.: SciB018
	Version and Date: Version 1.0, March 4, 2015

14. Any confirmed or suspected immunosuppressive or immunodeficient condition.
15. Receipt of blood or immunoglobulin transfusion six months prior to the first vaccine dose and during the course of the trial.
16. Unwilling or unable (in the judgment of the investigator) to comply with all the requirements of the protocol.
17. Participate in another clinical trial within 3 months prior to first vaccination (calculated from the previous study's last dosing date).

5.4 SUBJECT IDENTIFICATION

Each subject who signed the informed consent will be identified by a unique CRC internal identification number. Subjects who are dosed will receive an additional subject study ID number.

5.5 SCREENING FAILURES

Subjects who fail to meet the entrance criteria at any stage during the screening period are defined as screen failures. All screen failures will be documented on the screening log, which documents the screening number, subject's initials and reason(s) for screen failure. The screening log will be kept in the Investigators Site File.

Screen failure subjects will be withdrawn from the study and will not count towards the total enrolled or total eligible subjects.

5.6 REMOVAL, REPLACEMENT, OR EARLY WITHDRAWAL OF SUBJECTS FROM TREATMENT OR ASSESSMENT

Subjects are free to discontinue their participation in the study at any time and without prejudice to further treatment. The Investigator must withdraw any subject from the study if that subject requests to be withdrawn, or if it is determined that continuing in the study would result in a significant safety risk to the subject.

Subjects discontinued or withdrawn from the study will **not** be replaced after first dosing.

The subject's participation in this study may be discontinued due to the following reasons:

- Request of regulatory agency, or Sponsor or Principal Investigator
- Subject withdrew consent
- Adverse event (AE)
- Subject is unwilling or unable to continue the study or is lost-to-follow-up
- Subject is non-compliant with study procedures/study protocol
- Investigator decides that withdrawal from the study is in the best interest of the subject
- Subject needs medication not allowed in the protocol
- Any clinically significant change in subject's medical condition.

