6.3.3 Shipment of Samples to the Bioanalytical Laboratory

Samples will be shipped in a cold pack to the central laboratory on the same day it is drawn from the subject, as detailed in the lab manual provided by the Sponsor.

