5.6 REMOVAL, REPLACEMENT, OR EARLY WITHDRAWAL OF SUBJECTS FROM TREATMENT OR ASSESSMENT

Subjects are free to discontinue their participation in the study at any time and without prejudice to further treatment. The Investigator must withdraw any subject from the study if that subject requests to be withdrawn, or if the subject present positive serological marker of hepatitis B infection, or it is determined that continuing in the study would result in a significant safety risk to the subject.

Subjects discontinued or withdrawn from the study will **not** be replaced after first dosing. If insufficient number of subjects are expected to complete the study, recruitment of additional volunteers will be considered. Approval by the IRB will be required.

The subject's participation in this study may be discontinued due to the following reasons:

- Positive serological marker for hepatitis B infection
- Request of regulatory agency, or Sponsor or Principal Investigator
- Subject withdrew consent
- Adverse event (AE)
- Subject is unwilling or unable to continue the study or is lost-to-follow-up

	Protocol No.: SciB018
	Version and Date: Version 2.0, September 9, 2015 Amendment 1

- Subject is non-compliant with study procedures/study protocol
- Investigator decides that withdrawal from the study is in the best interest of the subject
- Subject needs medication not allowed in the protocol
- Any clinically significant change in subject's medical condition.

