2.4 Study Populations

Up to ninety two (92) healthy subjects will be enrolled in the study

Intent-to-Treat (ITT) Population includes all enrolled subjects who were vaccinated at least once with Sci-B-Vac™. The Safety population will be same as ITT population.

Modified Intent-to-Treat (mITT) population is a subset of the ITT set. This set will consist of all enrolled subjects who were vaccinated at least once with Sci-B-Vac™ and had at least one post vaccination follow-up visit, fully comply with the study protocol, had no violation of any of the inclusion/exclusion criteria and did not demonstrate an anamnestic response after the 1st administration of Sci-B-Vac. An anamnestic response revealed by Sci-B-Vac is defined as anti-HBs level above 6000mIU/ml (the highest titer recorded upon Sci-B-Vac 1st injection) in a subject with no detectable anti-HBs antibody at visits 1 and 2. Subjects who early terminated the study but reached the primary endpoint will be included as well. Subjects who did not complete the full-course of vaccination (i.e. 3 injections) and did not reach SPR will be excluded from the mITT set. This analysis set will serve as the primary analysis set for efficacy and safety inference.

Full Treatment (FT) set is a subset of the mITT analysis set and will consist of all subjects who were vaccinated 3 times with Sci-B-Vac™ and had at least one visit following the 3rd vaccination.

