2.7 Interim Analyses

The percent of subjects who achieved the primary endpoint will be tested at various time points. As soon as approximately 95% of the subjects (from at least 50 subjects) will be found seroprotected (having anti-HBs antibody concentrations $\geq 10\text{mIU/ml}$) then the primary efficacy endpoint will be achieved and the analysis will be considered a formal interim analysis and will be reported. A second interim analysis will be performed after all subjects have completed all three injections. Subjects who early terminated the study but reached the primary endpoint prior to termination will be included in the analysis.

Interim analysis reports will include all efficacy and safety information collected up to the interim analysis cut-off date. Exploratory endpoints (anti-pre-S1 and anti-pre-S2 testing) will not be included in the interim reports.

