4.4 Primary Endpoint Analysis

The primary endpoint of the study is the Seroprotection rate (SPR), defined as the proportion of subjects with anti-HBs antibody titer at least equal to 10mIU/ml, at Month 7 (i.e. one month after the third immunization with Sci-B-Vac™). In the first Interim Analysis the primary endpoint will be tested on month 4. Subjects early terminated from the study for any reason at any time while having an anti-HBs antibody concentrations ≥ 10 mIU/ml will be considered among those who met endpoint.

The principal analysis of the primary endpoint will employ a non-inferiority analysis [SAS PROC FREQ with binomial (noninf margin=0.09 p=(1- α) exact)] statement will be used for testing the below hypothesis:

H0: $P-p_0 \leq -\text{Margin}$

H1: $P-p_0 > -\text{Margin}$

Where p_0 , the assumed true SPR is 95% and the non-inferiority margin is 9.0%, employing that study will be considered successful if the lower bound of the (1- α) exact CI will be 86.0% or more.

The rate of responders will be calculated along with 95% confidence interval using Exact binomial method. The final population for statistical analysis will include only subjects who fully comply with the study protocol, have no inclusion/exclusion criteria violation and subjects who early terminated the study but reached the primary endpoint prior to withdrawal (mITT population).

Comparative analysis will be applied for baseline characteristics (such as gender, smoking status, age and BMI) between non seroprotected subjects (i.e. anti-HBsAg antibody<10), seroprotected subjects (ie. anti-HBsAg antibody ≥ 10 mIU/ml) and subjects with Anti-HBs ≥ 100 mIU/ml.

Age categories will be defined by intervals of 5 or 10. BMI will be defined <25 or ≥ 25 . Smoking status will be defined using 5 categories:

Never

Past-smoker;

Light smoker (up to 10 cigs/day)

Moderate smoker (10-19 cigs/day)

Heavy smoker (20 or more cigs/day) BMI categories will be defined <25 and ≥ 25

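### The SAP's primary set drops non-responders who leave or are judged non-compliant but keeps responders who leave, and nothing fixes membership before anti-HBs results are known

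*Protocol*

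**What the plan says.** Three places in the SAP decide who counts in the primary analysis.

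- SAP 2.4 requires mITT members to "fully comply with the study protocol, had no violation of any of the inclusion/exclusion criteria". It adds that "Subjects who did not complete the full-course of vaccination (i.e. 3 injections) and did not reach SPR will be excluded from the mITT set", while early terminators who reached the endpoint are kept.
- SAP 2.8 takes subjects who completed 12 months of follow-up, plus early terminators who had already met the endpoint.
- SAP 4.4 repeats the condition: "The final population for statistical analysis will include only subjects who fully comply with the study protocol". Full compliance is not defined, no decision maker is named, and no time is given by which the judgement must be made.

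Protocol v2.0 section 5.6 lists reasons for discontinuation that leave room for judgement: "Request of regulatory agency, or Sponsor or Principal Investigator", "Subject is non-compliant with study procedures/study protocol" and "Investigator decides that withdrawal from the study is in the best interest of the subject". These three reasons also stand in v1.0. Other parts of 5.6 changed in v2.0, notably the new reason of a positive hepatitis B marker.

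The design is open label with one arm. Anti-HBs is measured at every visit from Visit 2 (protocol 6.3.1). SAP 2.7 states that "The percent of subjects who achieved the primary endpoint will be tested at various time points".

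The protocol's own mITT (v2.0, 10.4.1) differs: it keeps anyone with one vaccination and one follow-up visit. SAP 2.4 also defines an ITT set of all vaccinated subjects, but SAP Appendix I plans the seroprotection tables by month on mITT and FT only.

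**The concern.** The SAP rules treat people who leave according to their titre. A subject below 10 mIU/ml who is withdrawn before the third injection leaves the denominator. So does one who is below 10 mIU/ml at Month 7 and is withdrawn before Month 12. A subject above the threshold who leaves on the same day counts as a success. Two separate problems follow.

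1. **Built-in bias.** Even with perfect masking and no discretion, failures who leave are deleted and successes who leave are counted. This can only raise the seroprotection rate (SPR).
2. **Room for titre-aware decisions.** If the people who judge withdrawal or compliance know the titre, a non-responder is easier to remove and a responder easier to retain. Nothing in the supplied documents prevents this order of events.

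Both act in the direction that qualifies the batch, and a single-arm trial has no comparator in which the same bias would cancel.

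**Working it through.** **Inputs.** Limit 86.0%, which is 95% minus the 9.0% margin (SAP 2.6, 4.4). Overall 5% level, two-tailed (SAP 3.1). Planned evaluable n=70 (SAP 2.6). Enrolment 84 (protocol v2.0, 5.1) or 92 (SAP 2.4). SAP 2.6 also refers to a one-sided 95% interval, so both readings are shown.

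**Formula.** The exact (Clopper-Pearson) lower bound for x successes in n is the a-quantile of Beta(x, n−x+1), with a=0.025 for the two-sided 95% interval and a=0.05 for the one-sided. Removing k non-responders changes x/n to x/(n−k).

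**The plan's own figures.** SAP 2.6 says n=70 gives a lower bound of at least 86.0% at an expected 0.95. 66/70 gives 86.01% two-sided and 87.40% one-sided, so the statement reproduces. The v1.0 power (86.1% at n=70, limit 82.5%, 95.86% interval) reproduces at 86.3% with a two-sided interval. Putting 0.0414 in one tail would give 94.0%, so v1.0 used the two-sided reading.

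**Effect of removals, two-sided 95% interval**

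| Planned n | Result | Lower bound | After 1 removal | After 2 removals |
|---|---|---|---|---|
| 70 | 65/70 | 84.11% fail | 65/69: 85.82% fail | 65/68: 87.64% pass |
| 84 | 78/84 | 85.10% fail | 78/83: 86.50% pass | not needed |
| 84 | 77/84 | 83.58% fail | 77/83: 84.93% fail | 77/82: 86.34% pass |
| 92 | 85/92 | 84.95% fail | 85/91: 86.20% pass | not needed |
| 92 | 84/92 | 83.58% fail | 84/91: 84.79% fail | 84/90: 86.05% pass |

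**One-sided 95% interval.** 78/84 already passes (86.39%). 65/70 fails (85.57%), and one removal is enough (65/69: 87.22%).

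**False-pass probability at a true SPR of 86%.** This is the binomial probability that the result passes when up to k non-responders may be removed, two-sided rule. At n=84 it is P(X≥79), P(X≥78) and P(X≥77) for k=0, 1 and 2. At n=92 it is P(X≥86), P(X≥85) and P(X≥84). At n=70 it is P(X≥66) for k=0 and k=1, and P(X≥65) for k=2.

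| n | k=0 | k=1 | k=2 |
|---|---|---|---|
| 70 | 2.5% | 2.5% | 6.1% |
| 84 | 1.7% | 4.1% | 8.4% |
| 92 | 2.0% | 4.5% | 8.9% |

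One-sided at n=70 the figures are 2.5%, 6.1% and 12.4%.

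**Contrast.** If every vaccinated subject stays in the denominator and non-responders count as failures, 65/70 remains a fail whatever is decided about withdrawal (84.11% two-sided, 85.57% one-sided).

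**The case against.** **Protocol 5.6 is not itself the defect.** This stands. Under the protocol's own mITT, a withdrawn non-responder with one follow-up visit stays in the denominator, so broad withdrawal reasons do no statistical harm there. The harm arises when SAP 2.4, 2.8 and 4.4 are applied on top.

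**Access to titres is not documented.** This also stands. A reader might infer that sponsor and site staff see each anti-HBs result as it arrives. The documents do not say so. Protocol 6.3.3 says "Samples will be shipped in a cold pack to the central laboratory on the same day it is drawn from the subject", which covers transport and not reporting; SAP 2.7 does not say who runs the checks; and the lab manual is not supplied. What can be said is that no supplied passage restricts access. The sentence about blinded data in protocol 11.5 concerns personal data protection and does not mention titres.

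**One removal is not always enough.** At the planned n=70 with the two-sided interval it is not. The flip also needs a result within one or two failures of the limit.

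**Safeguards exist.** Withdrawal reasons go in the CRF (protocol 5.7), the monitor documents deviations (11.7), deviations are listed (SAP 3.5), and SAP Appendix I has tables of discontinuation reasons and analysis populations. These make removals visible. They do not fix membership before titres are known, and no planned seroprotection table by month on the ITT set would show the effect.

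**The anamnestic-response exclusion in SAP 2.4 is also titre-based.** It removes subjects with very high titres, who are successes, so it does not help the batch pass.

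**Conclusion.** The point holds for the SAP's definition of the primary set. Membership rests on an undefined compliance judgement, depends in part on whether seroprotection was reached, and is not fixed before results can be known. One or two removals can turn a narrow fail into a pass: one at n=84 or n=92, two at n=70 under the two-sided interval, one at n=70 under the one-sided interval.

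The false-pass figures are worst cases. They assume a true SPR of 86%, a decision maker who knows the titres, and removals used only on non-responders and only when they help. They measure exposure and do not forecast conduct. A reader might infer that such removals are intended or likely; nothing in the documents supports that. The built-in bias needs none of these assumptions, but its size depends on how many non-responders leave, and the documents do not give that number.

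**What to change.** 1. **Fix membership without sight of titres.** In SAP 2.4, define full compliance and require a signed list of each subject's deviation, compliance and set-membership status before each interim analysis and before the final analysis. The list is made by people without access to post-baseline anti-HBs results. In protocol 6.3.3 and the lab manual, route those results only to the statistician who runs the SAP 2.7 checks and takes no part in the listed decisions. HBsAg and safety results reach the site as now. If the anamnestic rule is kept, apply it by program after the list is signed.
2. **Remove the dependence on outcome.** In SAP 2.4, 2.8 and 4.4, do not let membership turn on whether seroprotection was reached. Either use the protocol mITT (v2.0, 10.4.1) as the primary set, or report SPR on the ITT set already defined in the SAP. In both, count withdrawn non-responders as failures.

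Masking alone would leave the built-in bias, so both parts are needed.

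**Cost.** Wording in the SAP, the protocol and the lab manual; no new visits or tests. Site and sponsor see individual titres later, and the investigator should confirm that this is acceptable. A statistician outside the withdrawal and deviation decisions must be named, since the documents do not show one. The reported SPR may be slightly lower.

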5.7 HANDLING OF WITHDRAWALS

If a subject is withdrawn from the study or fails to return either at his/her request or at the Investigator's discretion, every effort should be made to determine the reason. This information will

	Protocol No.: SciB018
	Version and Date: Version 1.0, March 4, 2015

be recorded on the subject's case report form (CRF). All subjects who withdraw from the study prematurely, regardless of cause, should undergo all study termination assessments (see Section 6.1.11). It is vital to obtain follow-up data for any subject withdrawn because of an AE or abnormal laboratory test finding. In any case, every effort must be made to undertake safety follow-up procedures.

If withdrawal is caused by a Suspected Unexpected Serious Adverse Reaction (SUSAR), it will be reported to the institutional review board/independent ethics committee (IRB/IEC) and Sponsor.

5.8 TERMINATION OF STUDY BY SPONSOR

The Sponsor reserves the right to discontinue the study at any time for any reason. Such reasons may be any of, but not limited to, the following:

- Occurrence of AEs unknown to date in respect of their nature, severity, and duration or the unexpected incidence of known AEs
- Medical or ethical reasons affecting the continued performance of the study

Regulatory Authorities also have the right to terminate the study for any reason.

5.9 TERMINATION OF STUDY

A subject will be considered to have completed the study if he or she has completed all assessments at Month 12 of the study.

6 STUDY PROCEDURES AND SCHEDULES

The schedule of activities for this study is shown in Appendix A. No protocol-related procedures should be performed before subjects provide written informed consent. Study related events and activities including specific instructions, procedures, concomitant medications, dispensing of study drugs, and descriptions of AEs should be recorded in the appropriate source documents and CRF.

6.1 VISIT SCHEDULES

6.1.1 Visit 1 - Screening (within 4 weeks before Visit 2)

Subjects will sign an informed consent form and will be assessed for their eligibility to participate in the study.

The following screening assessments will be performed at pre-study for each subject:

- Medical history (including concomitant medications)
- Demographics (gender, date of birth)
- Vital signs: blood pressure and heart rate - supine, respiration rate (RR), oral body temperature
- Height
- Weight
- BMI (calculated as kg/m²)
- Physical examination

	Protocol No.: SciB018
	Version and Date: Version 1.0, March 4, 2015

- 12-lead ECG
- Laboratory safety screens as outlined in Appendix B
- For female subjects serum β HCG
- Serology tests as outlined in Appendix A
- Compliance with inclusion/exclusion criteria

The amount of blood drawn in this visit is approximately 31 ml.

6.1.2 Visit 2 - First Vaccine Administration: Month-0 (Day 1)

Dosing day will be designated "**Month 0, Day 1**".

The subjects will be admitted to the CRC in the morning of treatment. They will be interviewed by the CRC study personnel regarding change in concomitant medications or changes to their health status since the Screening visit. Female subjects will undergo a urine pregnancy test, and eligibility of inclusion/exclusion criteria will be reviewed.

Prior to dosing (within 60 min before vaccination), the following activities will be completed:

- Vital signs, measured following 3 min rest (sitting BP, HR, RR and oral temperature);
- A blood sample for serology and safety laboratory testing (18 ml) will be drawn.
- Urine sample will be collected for safety testing.

Vaccine administration: Each subject will receive the injection as described in Section 7.3. The time and date of vaccination will be documented in the CRFs and on the CRC Drug Administration Records.

After vaccination: Subjects remain in the CRC for approximately 1 hour after injection. Vital signs (sitting BP, HR, respiratory rate, and oral body temperature) will be measured at 60 (\pm 15) minutes after treatment, and recorded as appropriate.

Before discharge from the CRC a study physician will examine the injection site using a grading score (Appendix C).

The subjects will then be released from the CRC following a study physician's approval.

6.1.3 Visit 3 - Second Vaccine Administration: Month 1, (Week 4 \pm 3 days)

The second vaccination will take place 28 (\pm 3) days after the first vaccination (Visit 2). The previous injection site will be inspected before the second administration. Procedures will be identical to Visit 2.

